1 INTRODUCTION

1.1 Disease Background

Neuromyelitis optica (NMO; also known as Devic's syndrome) is a rare, chronic, autoimmune, inflammatory, demyelinating disorder of the central nervous system (CNS) characterized by attacks of predominantly optic neuritis (ON) and longitudinally extensive transverse myelitis (LETM). Commonly reported symptoms include unilateral and bilateral loss of visual acuity, ocular pain, loss of sensation, severe paraplegia, bladder and bowel dysfunction, paroxysmal tonic spasms of the trunk and limbs, and Lhermitte's phenomenon. Brain and brain stem involvement are rare but can occur, usually as an extension of a severe cervical myelitis, and may cause symptoms such as nausea, intractable vomiting, hiccups, and acute neurogenic respiratory failure (Wingerchuk et al, 1999; Misu et al, 2005). Up to 90% of patients with NMO have relapsing episodes of ON and myelitis rather than a monophasic course (Ghezzi et al 2004; Wingerchuk et al 1999). Relapses occur within 1 year of onset in 60% of patients and within 3 years in 90%. Relapses can be severe and result in blindness, paralysis, and even death due to neurogenic respiratory failure (Oh and Levy, 2012). Incomplete recovery from attacks is typical, and accumulative disabilities arise from the severity and frequency of attacks. By some estimates, within 5 years, > 50% of patients are blind in one or both eyes or require ambulatory help (Wingerchuk et al, 2007). Historically, mortality in NMO was as high as 30% at 5 years, but a more recent study suggests 9% at 6 years (Kitley, Leite et al, 2012).

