4.3.1.5 Independent Adjudication Committee

Three experts in NMO/NMOSD disease will constitute the independent AC. This committee has the mandate to evaluate each data set that is generated during the Assessment Visit and determine if an NMO/NMOSD attack occurred based on the clinical presentation, assessments, and the protocol-defined criteria for an NMO/NMOSD attack. The committee is completely independent and blinded to treatment assignments and/or to pertinent treatment

unmasking information (eg, B-cell counts, AQP4-IgG titers post-randomization) of study subjects, and to any decision made by the Principal Investigator regarding an NMO/NMOSD attack. The committee will use its judgement and clinical experience to make its determination based on the data provided. The committee will review the same data that are available to the Principal Investigator when he/she makes his/her determination about the attack. In exceptional cases, determined and justified by the committee as such, the committee can request to review additional data that is essential to make a determination. The committee's role, function and procedures are governed by a separate charter.

The data from all subjects who are assessed at an Assessment Visit due to a new symptom(s) or worsening of an existing symptom(s) related to NMO/NMOSD will be sent for adjudication by the AC regardless of whether the Principal Investigator has determined that an NMO/NMOSD attack has occurred. Furthermore, the AC will not receive information about which protocol attack criterion was met and the rescue medication utilized.

Determination of an NMO/NMOSD attack by the AC is for the purpose of determining which events will be included in the primary analysis. It will NOT affect the rescue therapy that a subject may receive.

Only subjects in whom the attack was determined by the AC will be given the option to enter the OLP.

In addition, the data set that was generated and used by the Principal Investigator to assess the symptom(s) that were determined not to be related to NMO/NMOSD in the RCP, will be delivered to the AC for a non-real-time review.

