4.8.3 Efficacy

4.8.3.1 Primary Efficacy Analysis

The following are the null and alternative hypotheses associated with the primary endpoint:

$$H_{01}: HR^+ = 1 \text{ vs } H_{11}: HR^+ \neq 1,$$

$$H_{02}: HR^{ALL} = 1 \text{ vs } H_{12}: HR^{ALL} \neq 1,$$

where HR^+ indicates the hazard ratio of AC-determined NMO/NMOSD attack for MEDI-551 relative to placebo in AQP4-IgG seropositive subjects. HR^{ALL} denotes the same quantity for the ITT population. The treatment effect in the seropositive cohort will be defined as the relative reduction in HR^+ ; ie, $100 \times (1 - HR^+)$. A value of $HR^+ < 1$ or a positive value of relative reduction will indicate the efficacy of MEDI-551 compared to placebo in the seropositive cohort. Similar interpretations will hold for HR^{ALL} . For the current study, the target treatment effect of 60% implies a hazard ratio (HR) of 0.4.

For the AQP4-IgG seropositive cohort, the treatment effect will be assessed using the Cox proportional hazards model with treatment indicator (MEDI-551 or placebo) as an explanatory factor; whereas for the ITT population, the model will also include serostatus as an additional explanatory factor. The HR of MEDI-551 versus placebo will be estimated together with its associated 95% confidence interval (CI). The SAS PROC PHREG will be used for fitting this model. Subjects who complete Day 197 of the RCP or discontinue the study before Day 197 for reasons other than an AC-determined NMO/NMOSD attack will be censored in this model at the time of the Day 197/discontinuation visit. See Section 4.8.9 for details regarding Type I error control.

An indicator variable for Japan versus non-Japan region will not be included in the Cox regression model due to the low number of anticipated Japanese subjects. An evaluation of

consistency of treatment effect in Japanese subjects with that observed in the global study will be determined.

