5.2 Definition of Serious Adverse Events

An SAE is any AE that:

- Results in death (for the purposes of this protocol, this includes NMO/NMOSD disease progression or attack)
- Is immediately life-threatening
- Requires inpatient hospitalization or prolongation of existing hospitalization
- Results in persistent or significant disability/incapacity
- Is a congenital anomaly/birth defect in offspring of the subject
- Is an important medical event that may jeopardize the subject or may require medical intervention to prevent one of the outcomes listed above

Medical or scientific judgment should be exercised in deciding whether expedited reporting is appropriate in this situation. Examples of medically important events are intensive treatment in an emergency room or at home for allergic bronchospasm, blood dyscrasias, or convulsions that do not result in hospitalizations; infection that requires treatment with IV antibiotics; or development of drug dependency or drug abuse.

For the purposes of this protocol, NMO/NMOSD disease progression or attack that do not result in death, but meet any of the other above listed SAE criteria, will not be reported as an SAE unless it occurs during the screening period or in the SFP.

NMO/NMOSD disease progression or attacks that result in death will be reported as SAEs.

All occurrences of NMO/NMOSD attacks will be carefully monitored by the site staff and the Sponsor to ensure these are identified in the required reporting timeline.

Additionally, hospitalization for any procedure resulting from an NMO/NMOSD attack will *not* be reported as an SAE (eg, PLEX that could result in hospitalization).

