6.3 Study Timetable and End of Study

The end of the study ("study completion") is defined as the date of the last protocol-specified visit/assessment (including telephone contact) for the last subject in the study. This will occur when the last subject completes the 52-week SFP.

An individual subject will be considered to have completed the RCP if the subject was followed through Day 197 or experienced an NMO/NMOSD attack as determined by the AC, regardless of the number of doses the subject received. Additionally, all subjects enrolled in the RCP at time that the 67th AC-determined attack is confirmed, or at the time the Sponsor discontinues enrollment upon recommendation of the independent DMC based on evidence of efficacy and safety, will also be considered as completers, regardless of the number of doses the subject received, provided the subject completes the Day 197/EDV visit. A subject will be considered to have completed the OLP if the subject participated for the duration of the OLP as per Section 3.1.1.4. A subject will be considered to have completed the SFP if the subject was followed for 52 weeks (12 months) after the last dose of investigational product. Subjects will be considered not to have completed a study period if consent was withdrawn, death occurred, or the subject was lost to follow up.

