3.4.1.3 Primary Efficacy Analysis

The following are the null and alternative hypotheses associated with the primary endpoint:

$$H_{01}: HR^+ = 1 \text{ vs } H_{11}: HR^+ \neq 1,$$

$$H_{02}: HR^{ALL} = 1 \text{ vs } H_{12}: HR^{ALL} \neq 1,$$

where HR^+ indicates the hazard ratio of AC-determined NMO/NMOSD attack for MEDI-551 relative to placebo in AQP4-IgG seropositive subjects. HR^{ALL} denotes the same quantity for the ITT population. The treatment effect in the seropositive cohort will be defined as the relative reduction in HR^+ ; ie, $100 \times (1 - HR^+)$. A value of $HR^+ < 1$ or a positive value of relative reduction will indicate the efficacy of MEDI-551 compared to placebo in the seropositive cohort. Similar interpretations will hold for HR^{ALL} . For the current study, the target treatment effect of 60% implies a hazard ratio (HR) of 0.4.

For the AQP4-IgG seropositive cohort, the treatment effect will be assessed using the Cox proportional hazards model with treatment indicator (MEDI-551 or placebo) as an explanatory factor; whereas for the ITT population, the model will also include serostatus as an additional explanatory factor. The HR of MEDI-551 versus placebo will be estimated together with its associated 95% CI. The SAS PROC PHREG will be used for fitting this model. Subjects who complete the Day 197 visit of the RCP or discontinue the study before Day 197 for reasons other than an AC-determined NMO/NMOSD attack will be censored in this model at the time of the Day 197/discontinuation visit.

An indicator variable for Japan versus non-Japan region will not be included in the Cox regression model due to the low number of anticipated Japanese subjects. An evaluation of consistency of treatment effect in Japanese subjects with that observed in the global study will be determined.

The data cutoff date for the primary analysis will be when the last subject completes the discontinuation visit following the 67th AC-determined attack, or after all subjects complete the RCP if 67 AC-determined attacks do not occur, or when the last subject completes the discontinuation visit following discontinuation of enrollment upon recommendation of the DMC based on evidence of efficacy and safety. Subjects who are in the RCP when a total of 67 AC-determined NMOSD attacks have occurred, or when enrollment is discontinued upon

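### A subject who dies of an NMO/NMOSD attack before any Assessment Visit starts cannot be a primary event and is censored, with no defined censoring date

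*Protocol*

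**What the plan says.** - **Censoring.** Under Protocol 4.8.3.1, subjects who "discontinue the study before Day 197 for reasons other than an AC-determined NMO/NMOSD attack will be censored in this model", and the time used is the Day 197 or discontinuation visit. SAP 3.4.1.3 has the same rule ("discontinue the study before Day 197 for reasons other than an AC-determined NMO/NMOSD attack will be censored"). Neither names death. SAP 3.4.1.2 rules out imputation for the primary analysis.
- **What qualifies as an event.** Protocol 4.8.3.1 and SAP 3.4.1.1 admit an AC-determined attack only if an Assessment Visit was scheduled within 120 hours of the symptom report and the assessments were done within 10 days of that visit. SAP 3.4.1.1 sets the onset day at the start of that visit.
- **AC remit.** Protocol 4.3.1.5: "This committee has the mandate to evaluate each data set that is generated during the Assessment Visit". In exceptional cases "the committee can request to review additional data that is essential to make a determination". A separate charter governs procedure.
- **Death elsewhere in the plan.** Protocol 1.1: "Relapses can be severe and result in blindness, paralysis, and even death due to neurogenic respiratory failure". Protocol 5.2: "NMO/NMOSD disease progression or attacks that result in death will be reported as SAEs". Protocol 6.3: "Subjects will be considered not to have completed a study period if consent was withdrawn, death occurred, or the subject was lost to follow up".

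**The concern.** Death caused by an attack is the most severe form of the primary endpoint, not an unrelated competing event. The safety section recognises it, and Protocol 5.5 requires the SAE report within 24 hours. The information is therefore collected, but no rule carries it into the primary endpoint.

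Censoring such a subject assumes that leaving says nothing about attack risk, when in fact the attack is why the subject left. The resulting bias can go either way. Losing fatal attacks on placebo pulls the hazard ratio toward 1. Losing them on MEDI-551 makes the drug look better than it is.

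**Working it through.** **1. Following the rules for two cases**

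| | Attack fatal before any Assessment Visit | Visit started, death follows |
|---|---|---|
| Data set for the AC | none from a visit; AC may ask for other data | yes, possibly partial |
| Onset day (SAP 3.4.1.1) | none | start of the visit |
| 120-hour/10-day rule | cannot be met | can be met: the SAP asks only for the assessments that were needed |
| If the window is missed | still no event | counted in SAP sensitivity analysis 6a if AC-determined |
| Primary model | censored, no date defined | can be an event |

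Only the first column is a gap. The visit may start up to 72 hours after the symptom report (Protocol 4.2.3), so the case is possible.

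**2. The plan's own figure (Protocol Appendix 9)**

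E = [(1.960 + 1.282)/ln 0.4]² × 16/3 = 66.75, rounded up to 67. This reproduces the plan, and power at 67 events is 90.1%. Nothing here changes the 67-event target.

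**3. Follow-up in the RCP**

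Inputs are from Appendix 9: 252 subjects, 80:20 serostatus, 3:1 allocation, F = 197/365. Person-years per group = n(1 − e^(−λF))/λ.

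| Group | n | λ per year | Person-years | Expected attacks |
|---|---|---|---|---|
| Placebo, seropositive | 50.4 | 1.5 | 18.6 | 28.0 |
| Placebo, seronegative | 12.6 | 1.0 | 5.3 | 5.3 |
| MEDI-551, seropositive | 151.2 | 0.6 | 69.7 | 41.8 |
| MEDI-551, seronegative | 37.8 | 0.4 | 18.4 | 7.3 |

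The total is about 112 person-years, of which 23.9 are on placebo. The placebo share of attacks is 33.2/82.4 = 0.40, so 67 attacks split about 27 placebo and 40 MEDI-551.

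**4. Deaths from all causes**

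The mortality figures are from Protocol 1.1. A constant hazard is my assumption.

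- 9% at 6 years: −ln(0.91)/6 = 0.0157 per year; × 112 = 1.8 deaths. With equal mortality by arm, placebo has 0.0157 × 23.9 = 0.4 and MEDI-551 about 1.4.
- Historical 30% at 5 years: −ln(0.70)/5 = 0.0713 per year; × 112 = 8.0 deaths.
- If attacks did not shorten follow-up, the totals would be 2.1 and 9.5.

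These are ceilings. The documents give no attack-related share, and deaths before any visit are a fraction of that share. Even if every one of the 1.8 deaths were an attack death split like the attacks, placebo would have 1.8 × 27/67 = 0.7.

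**5. Effect on the hazard ratio (illustrative extreme)**

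Person-time is held fixed.

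- Two placebo attack deaths censored: 0.40 × 27/25 = 0.43.
- Two MEDI-551 attack deaths censored: 0.40 × 38/40 = 0.38.

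For scale, the 95% interval around 0.40 with 27 and 40 events uses SE = √(1/27 + 1/40) = 0.249 and runs from 0.25 to 0.65. If two of the 67 events were lost and not replaced, power would fall from 90.1% to 89.2%.

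**The case against.** The strongest case against is that the gap is very small and largely covered elsewhere. Several parts of it stand.

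- **The AC is not confined to Assessment Visit data.** A reader might infer that it is, but Protocol 4.3.1.5 allows requests for more, and the charter is not available here. It cannot be shown that the AC has no procedure for fatal cases. This does not close the gap, because the window and the onset definition both still need a visit.
- **Fatal attacks in general are not lost.** A reader might infer this too. Onset is dated at the visit, before any later death, and a visit cut short can still qualify.
- **A censored subject is not scored as completing attack-free.** Such a subject contributes time only up to censoring.
- **Other analyses would catch some cases.** The time to attack or rescue therapy analysis (Protocol 4.8.7, SAP 3.5.4) counts a subject who received rescue therapy. The investigator-determined attack model (SAP 3.5.4) may count one. Sensitivity analysis 3 counts every premature discontinuation as an event. Deaths are tabulated with reasons (SAP 3.3.1), and the Data Monitoring Committee follows drop-out case by case (Protocol 4.8.8).

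None of these is the primary test, and analysis 3 pools attack deaths with every other drop-out. SAP sensitivity analysis 4, read literally, censors a premature discontinuer without a later attack at Day 204, even if the subject died on Day 30.

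One further point stands in part. The endpoint requires a Table 11 criterion, and the protocol's change log records the wider analysis window as agreed with the FDA. Attribution from incomplete records is a softer event definition, which is why a sensitivity analysis without those deaths belongs in the fix.

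**Conclusion.** The point holds for attacks that kill before any Assessment Visit starts. For those subjects the written rules give no onset day, no qualifying event and no censoring date, and the primary model treats the departure as non-informative.

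The expected size is small: at most about 1.8 deaths at the more recent mortality figure, about 0.4 of them on placebo. Two censored placebo attack deaths would be about five times the expected all-cause number in that arm, so 0.43 and 0.38 mark an extreme, not a forecast. A reader might infer that the primary result is at risk. The documents do not support that, since even the extreme shift lies well inside the sampling error of the hazard ratio.

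These figures assume constant mortality, equal mortality by arm, the planning attack rates and full enrolment of 252. The DMC-recommended enrolment stop in Protocol Amendment 6 would only reduce them. The rule is still worth fixing: it concerns the worst form of the endpoint, it can bias in either direction, and it should not be settled after a case is known by arm.

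**What to change.** In Protocol 4.8.3.1 and SAP 3.4.1.1 and 3.4.1.3, with a matching line in the AC charter, and before unmasking:

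1. Send every death in the RCP to the masked AC with the SAE records available.
2. Count a death that the AC attributes to an NMO/NMOSD attack as a primary event. Date it at documented symptom onset, or at death if onset is unknown, and exempt it from the 120-hour/10-day rule.
3. Censor all other deaths at the date of death, and apply the same limit in SAP sensitivity analysis 4.
4. Report a sensitivity analysis of the primary endpoint without the attributed deaths.

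The cost is one event rule, one censoring date and a charter line. No new visits are needed and the 67-event target is unchanged. The downside is attribution from incomplete records, and an onset date set differently from other events, in very few cases.

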4.8.3.2 Additional Analyses of the Primary Endpoint

An estimate of the cumulative event rates through the end of the RCP will be calculated using the Kaplan-Meier (KM) method. Graphical displays of KM estimates and cumulative incidence estimates will be presented by treatment group.

The following sensitivity analyses of the primary endpoint will be performed:

- 1 Analysis using the Cox regression model and the following baseline characteristics and treatment as exploratory variables:
 - Number of NMO/NMOSD relapses prior to randomization
 - Baseline EDSS score
- 2 Analysis similar to primary analysis but considering only unanimous AC-determined NMO/NMOSD attacks (all 3 adjudicators agree) as events, remaining subjects will be considered as censored.
- 3 Analysis similar to primary analysis but also considering subjects who prematurely discontinue the RCP without experiencing an AC-determined NMO/NMOSD attack as treatment failures (events); remaining subjects will be considered as censored.
- 4 Sensitivity analysis will be conducted to assess the impact of the loss of any AC-determined attacks outside of the identified assessment window in the primary analysis.

4.8.3.3 Secondary Efficacy Analyses

Secondary endpoints 1 through 4 presented in Section 2.2.2 for AQP4-IgG seropositive cohort will be analyzed as follows:

- Treatment effect for secondary efficacy endpoints based on EDSS worsening will be assessed using a logistic regression model with treatment and baseline EDSS as explanatory variables. The percentage of subjects meeting the endpoints, odds ratios, p-value, and 95% CIs of the odds ratios will be presented.
- The treatment effect for the low-contrast visual acuity measured by change from baseline in low-contrast Landolt C Broken Rings Chart binocular scores will be assessed using an analysis of covariance model using treatment and baseline Landolt C Broken Rings Chart binocular score as explanatory variables.
- The treatment effect for the secondary efficacy endpoints based on the cumulative number of active MRI lesions and number of NMO/NMOSD-related in-patient hospitalizations will be tested using Negative Binomial regression with treatment as an explanatory variable.

Similar analyses will be performed for the ITT population by extending the above mentioned models to include an indicator variable for serostatus as well.

See Section 4.8.9 for details regarding Type I error control.

Annualized attack rate (total number of AC-determined NMO/NMOSD attacks normalized by person-years) during any exposure to MEDI-551 will be summarized descriptively.

4.8.3.4 Subgroup Analyses

Consistency of treatment effect measured by primary and key secondary efficacy endpoints in the following subgroups will be investigated as follows:

- Sex (male vs female)
- Baseline EDSS (< 5 vs ≥ 5)
- Number of prior NMO/NMOSD relapses (< 2 vs ≥ 2)
- Disease duration category (< 5 years vs ≥ 5 years)
- AQP4-IgG serostatus (positive vs negative) as determined at screening

The nominal p-value and 95% CIs of treatment effect will be provided for each subgroup analysis.

4.8.4 Safety

4.8.4.1 Analysis of Adverse Events

The safety and tolerability of MEDI-551 will be assessed at completion of the study primarily by summarizing TEAEs including TESAEs. The occurrence of TEAEs will be collected and

summarized from the commencement of infusion of investigational product through the end of study. Treatment-emergent AEs and SAEs will be summarized by system organ class and preferred terms, by severity, and by relationship to the investigational product. For the OLP, the rate of AEs normalized by patient-years may be provided.

4.8.4.2 Analysis of Clinical Laboratory Parameters, Physical Examination Findings, and Vital Sign Measurements

Laboratory measurements as well as their changes from baseline at each collection time point and shift from baseline if applicable will be summarized descriptively. Significant physical examination findings and vital sign measurements will also be summarized using descriptive analyses.

4.8.5 Patient-reported Outcomes

4.8.5.1 Short Form-36 Health Survey

Treatment effect for the PRO endpoint based on SF-36 PCS (4-week recall) change from baseline at the last visit of the RCP will be tested using an analysis of covariance model using treatment and baseline SF-36 PCS score as explanatory variables. Similar analysis will be done for SF-36 MCS.

For the 8 remaining domains, summaries of change from baseline will be presented.

